8.2.1. Baseline Descriptives

Baseline descriptive data on demographics (gender, age, marital status, employment status, education level), health literacy) will be presented overall and for both groups separately. This will help to see whether the 2 groups were comparable at baseline.

8.2.2. Primary outcome

The primary outcome is the Spielberg state-trait anxiety index (STAI). Questionnaires that were not completed in the required timeframes will be treated as missing data:

- Baseline within 1 week of CT appointment
- Start of treatment on day of treatment
- End of treatment on day of treatment

Anxiety scores will be compared at each time point between the two groups for a statistically significant difference. The 2nd and 3rd timepoints will use baseline-corrected anxiety scores. Some additional analyses (including sensitivity analyses) on the primary outcome will also be conducted:

- a. The effectiveness of the intervention may vary across different subgroups of patients (e.g. age, education level). Therefore, supplementary statistical analyses are proposed in which it is tested if there is a statistical interaction between socio-demographic data and the primary outcome. This will include health literacy level measured at baseline.
- b. Any baseline variables that appear, by chance, to differ between the groups will be added in as covariates.
- c. Whether or not the patient has had previous radiotherapy will be added as a covariate.
- d. Longitudinal analysis of anxiety scores at all three time points to assess variation across treatment
- e. Proportions of high and low anxiety scores in each group at each time point.

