3.3. Duration of patient participation

The duration of patient participation will vary depending on their individual treatment regime. It is expected that there will be a two-week interval between consent and baseline, and the patients' first treatment (and intervention for those randomised to receive it). Subsequently, follow-up will be between 5 days and 6 weeks from the first treatment to the last treatment. End of patient participation will be defined as the completion of data collection for the last patient followed-up in the study.

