4.1. Primary outcome measure

The primary outcome measure for this study is patient-reported anxiety utilising a short form of the state scale of the Spielberger State-Trait Anxiety Index (STAI)⁵⁸. The STAI is one of the most used and cited measures of anxiety, with over 10,000 citations for Spielberger's two studies on the STAI^{58,59}. It has been used widely in radiotherapy settings. Short forms of the STAI have been investigated to create more clinically usable tools. These have been shown to perform well versus the full STAI^{60–62}. The STAI6 will be utilised here, as used by Marteau et al⁶⁰.

Anxiety will be measured at three timepoints:

- a. Baseline (after patient consent and enrolment on the trial)
- b. First treatment appointment, before treatment.
 - a. For patients on the intervention arm, this will be after the physicist consultation but before treatment
- c. End of treatment, before the last radiotherapy treatment

Scores range from 20 to 80, and a score of 40 is commonly used to differentiate between high and low anxiety⁶³. Scores at timepoints 1 & 2 will be corrected for baseline scoring for each participant, and the average (mean) score across both trial arms compared.

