6.2.1.1. Remote / telephone consent

Due to the cross-site nature of this study, it is feasible that an appropriately delegated member of the research team is not available to obtain participant consent. Alternatively, the participant might require further time to consider the study information. In these circumstances, if the participant wishes to join the study:

- The participant will go home with a copy of the PIS and the baseline questionnaire
- A member of the research team will contact the participant via telephone to discuss the study and obtain consent.
- Once consent has been obtained, the participant will complete the baseline questionnaire and bring with them to their first radiotherapy appointment (to maintain required timelines for data collection outlined below).

Telephone consent will be undertaken in line with the following:

- A telephone consent form will be used.
- The participant will be asked to complete a written Consent form at their next visit.
- The participant will receive copies of all consent forms, to include the telephone consent form.

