6.2.2. Baseline data

After eligibility has been confirmed and written consent obtained, and prior to randomisation, patients will be provided with a baseline questionnaire packet to be completed, and a member of the research team will complete the baseline case report form (CRF).

- Sociodemographic information collected from either medical records or selfreported by the participant.
 - Contact details, and preferred method of contact (to facilitate sending of appointments and questionnaire reminders).
 - o Year of birth
 - o Gender
 - Education level
 - Marital status
 - Employment status
 - Whether the participant deems English to be their 'first' or 'second' language
 - Clinical information collected from medical records
 - Area/site of treatment
 - Number of radiotherapy treatments (fractions) referred.
 - Has the participant had previous radiotherapy?
 - Has the participant been scanned with particular motion management, e.g. deep inspiration breath hold (DIBH)?
- Patient-reported anxiety STAIS6 questionnaire
- Health literacy assessment
- EQ-5D-5L questionnaire
- Information and communication questions
- Technical satisfaction questions

Ideally the participant-reported data will be collected on the day of consent, however it is acknowledged this may not be possible in all cases. This must be completed within 1 week of the CT appointment, either by post or electronically.

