6.3. Randomisation

Following completion of baseline information collection, a member of the research team will randomise the participant to one of the two treatment arms: physicist consultation or standard of care.

Patients will be randomised in order to minimise systematic bias, using a secure web-based system Sealed Envelope (https://www.sealedenvelope.com/simple- randomiser/v1/trials/rapport), certified as meeting ISO/IEC 27001 standards and the NHS England Data Security and Protection Toolkit.

Participants will be allocated to intervention group or to the control group in a 1:1 ratio. Randomisation will be stratified by gender. This is a surrogate for treatment site: the most common radiotherapy treatment sites (particularly at RWRC) are breast and prostate cancer. However, to ensure approximately equal distribution of treatment sites in each arm and avoid problems of low numbers of less common treatment sites, gender has been chosen has the stratification criteria. It is acknowledged that with the low sample size required in this study, distribution is likely still to be unequal but there is little evidence that the primary outcome varies by gender.

Upon randomisation, each participant will be assigned a unique Trial Number which will be used as the principal identifier on trial data collection forms and questionnaires. The research team member will disclose the allocation to the participant and will ensure the allocation is followed as described below.

6.4. **Provision of Treatment**

Following allocation, the participant will be informed of which trial arm they have been randomised to. Where required, the consultation will be booked by the PI or delegate and the patient informed what time this will be (as it will not be on their routine appointment list given at the CT appointment). If possible, a reminder will be sent via the DoctorDoctor service.

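### Section 8.2.2 treats a baseline STAI completed more than one week after CT as missing even when it precedes randomisation, which gives up usable data in a 60-patient trial

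*Protocol*

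**What the plan says.** Section 8.2.2 sets the rule for the primary outcome: "Questionnaires that were not completed in the required timeframes will be treated as missing data". The baseline line under it reads "Baseline within 1 week of CT appointment". It does not refer to randomisation and makes no exception for a form completed before it.

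Section 6.2.2 has the same limit for data collection: "This must be completed within 1 week of the CT appointment, either by post or electronically". It gives no reason for one week, and it accepts that completion on the day of consent will not always be possible.

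Section 6.3 fixes the order of events: "Following completion of baseline information collection, a member of the research team will randomise the participant". It sets no time limit from CT and asks for no check that the form was in window.

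Section 3.3 gives the time available: "It is expected that there will be a two-week interval between consent and baseline, and the patients' first treatment". Section 7.3 places the consultation on the first treatment day.

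On the use of baseline, Section 8.2.2 says "The 2nd and 3rd timepoints will use baseline-corrected anxiety scores". Section 4.1 says the post-baseline scores "will be corrected for baseline scoring for each participant".

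Section 6.2.1.1 provides for patients who need more time, or for whom no delegated staff member is available at CT. They take the questionnaire home and consent later by telephone. Then: "Once consent has been obtained, the participant will complete the baseline questionnaire and bring with them to their first radiotherapy appointment".

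**The concern.** A baseline used to correct later scores has to precede randomisation and the intervention. The rule in 8.2.2 does not test for that. It tests distance from CT. A patient who completes the form on day 9 and is then randomised has a score that precedes both allocation and consultation, yet 8.2.2 sets it to missing. Both post-baseline comparisons rely on that score, so one late form affects two comparisons even when both later questionnaires are complete and on time.

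The telephone-consent route makes this foreseeable. The week starts at CT, so time spent waiting for a delegated member of staff, or thinking the study over, comes out of the patient's window. The trial plans to recruit 60 patients against a requirement of 54, which leaves little room to set aside observed data.

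**Working it through.** **1. Can the case arise under the text?**

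- 6.2.2 and 8.2.2: the form is late if completed more than 7 days after CT.
- 6.3: randomisation follows baseline collection, with no stated limit from CT.
- 3.3: first treatment is about two weeks after consent and baseline.

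A form completed after day 7 can therefore still precede both randomisation and the first-day consultation. Nothing in 6.3 or 8.2.2 excludes or rescues it.

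**2. The plan's own figure**

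Inputs from Section 8.1: difference 10, SD 13, two-sided 0.05, 80% power, 1:1 allocation, 10% over-recruitment.

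Normal approximation per arm: n = 2 × (1.960 + 0.842)² × 13² / 10² = 26.5, rounded up to 27, so 54 in total. With the allowance, 54 / 0.90 = 60. The protocol's 54 and 60 are reproduced. The exact t calculation needs 28 per arm (56 in total), which is why power at 54 comes out just under 80% below.

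**3. Room in the allowance**

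60 − 54 = 6 patients. Section 8.1 intends these 6 to cover non-response, missing data and attrition together. If late baselines were the only loss, the allowance would absorb up to 6 of them (10%).

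**4. Power as the analysed number falls**

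With n per arm, the standard error is 13 × √(2/n), the noncentrality is 10 divided by that, and power is taken from the noncentral t with 2n − 2 degrees of freedom.

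| Analysed | Lost from 60 | n per arm | Standard error | Noncentrality | Power |
|---|---|---|---|---|---|
| 60 | 0 | 30 | 3.357 | 2.979 | 83.4% |
| 54 | 6 | 27 | 3.538 | 2.826 | 79.2% |
| 50 | 10 | 25 | 3.677 | 2.720 | 76.0% |
| 48 | 12 | 24 | 3.753 | 2.665 | 74.2% |

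The table counts losses from all causes. The protocol does not say how many baselines will be late, so the rows for 50 and 48 are assumed illustrations, not forecasts. They also assume that a patient with a missing baseline drops out of the comparison, which an SAP could prevent.

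**The case against.** The strongest reply is that the rule is clear, prespecified and consistent. Sections 6.2.2 and 8.2.2 state the same week, and 6.3 follows directly on the section that contains it. A form completed on day 9 already breaches a mandatory limit, and Section 10.6 is evidently meant to rule out planned deviations. Section 6.2.1.1 says its arrangement is there to keep to the required timelines, and 8.2.2 tests when the form was completed, not when it was returned. A window on state anxiety also has a plausible purpose: a form filled in close to first treatment may measure something different from one filled in near CT.

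Much of this stands. There is no contradiction between sections, late completion is a deviation and not the planned pathway, and posting a form back does not by itself make it late. It cannot be said that distance from CT has nothing to do with validity. But the protocol gives no reason for one week, and 6.3 does not expressly bar randomising the patient, so the case can still occur.

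Two stronger readings are tempting. One is that the rule biases the comparison, since slower deciders and remote returners may differ in anxiety. The documents do not support that: for a form completed before randomisation, lateness precedes allocation, so exclusion should not by itself favour either arm. What narrows is the population analysed. The other is that such patients are necessarily lost from the primary analysis. The text says their baseline is treated as missing, not that they are excluded. The SAP, which is not shown, could impute or model it, and the longitudinal analysis listed in 8.2.2 could use their later scores. Even so, an estimate would stand in for a score that was actually observed.

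**Conclusion.** The point holds as an inexpensive improvement to the missing-data rule, not as an error that invalidates the analysis. As written, 8.2.2 discards an observed baseline that precedes randomisation. The patient's two corrected scores then cannot be computed from observed data unless the SAP supplies the baseline another way. The cost is precision and departure from analysing all randomised patients.

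The size is unknown because the late rate is not given. Up to 6 late forms fit within the allowance if nothing else is lost. Every other loss uses up the same margin. Once it is exhausted, power drops from about 79% at 54 analysed to 76% at 50 and 74% at 48. These figures rest on the protocol's difference of 10 and SD of 13, equal arms, and no recovery of the missing baseline.

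**What to change.** Change the baseline line in 8.2.2 so that:

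- any baseline dated before randomisation, and so before the consultation, is kept in the primary analysis;
- a baseline completed after randomisation is treated as invalid;
- one week from CT remains as an operational target;
- the primary analysis is repeated, restricted to baselines completed within the week, as a sensitivity analysis.

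Record the completion date on the questionnaire. This matters most for the telephone-consent route, where the form is brought in on the day of first treatment, and its date has to show that it was completed before randomisation. The day-of-treatment rules for the other two timepoints can stay as they are.

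The cost is one revised line, one date field and one sensitivity analysis. The downside is slightly more variable timing of baseline relative to CT and first treatment, which the restricted analysis would help to assess.

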8. STATISTICS AND DATA ANALYSIS

8.1. Sample size calculation

Advice on the sample size calculation has been sought from [name], Principal academic in healthcare statistics at Bournemouth University.

The study is powered to detect a 10-point difference in patient-reported anxiety on the STAI. There is evidence that this is the minimally important difference (MID)^{18,42,66}. An estimate of standard deviation was made from work by Burmeister⁴² and Atwood³⁶ in similar radiotherapy populations, both studies used the STAI to measure patient anxiety. Atwood found standard deviations ranging from 10.2-15.6, whilst Burmeister found a lower standard deviation of 8.1. A standard deviation of 13 has been chosen to represent an average within the range of observed values from Atwood.

Based on an unpaired t-test with two groups of equal size, assuming 80% power, a twosided 0.05 significance level, a standard deviation of 13 and a mean difference of 10 points in patient-reported anxiety, a total sample size of 54 (27 in each group) is required. The study will over-recruit by 10% to allow for non-responders, missing data, or attrition (dropout). Therefore, the study will aim to recruit 60 patients in total (30 in each group) over a 1year recruitment period. This gives a similar sample size to the work of Atwood, and a sample size 1.5 times larger than Burmeister.

This sample size is also in the region of that calculated by an independent method (using the varying-slope varying-intercept model). Whilst this doesn't consider the repeated timepoints as independent, it represents a worst-case scenario. The details of this calculation are in Appendix 1, but the calculated sample size is 76 (although this doesn't account for attrition), slightly larger than the sample size calculated but of the same magnitude.

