12. APPENDICIES

12.1. Appendix 1: Independent Sample Size Calculation

The following is provided by [name].

Similar to the currently proposed study, [42] also describes itself as a two-group repeated measures design with patients modelled as random effects and patient visits as the repeats. While the model is not explicitly stated we can postulate a similar model here that captures the current scenario and explicate in more detail its different components and the assumptions we will make. With a repeated measures-type design we can choose to fit the data using a varying-slope varying-intercept model i.e. $y_{i,t} \sim N(\alpha_i + \beta_i t, \sigma_v^2)$ where j is patient and t indexes time while the variance term reflects a combination of error terms deriving from measurement error, variation in the STAI and departures for each patients' repeated data from the assumed linear model. We can further assume that the anxiety treatment will affect the slope but not the intercept (since at the baselinfiguree time zero there is no treatment). From [36], we can compute that the slope for controls is -.2 and the slope for the intervention group is -4.85. We can also derive the mean of the control group (at baseline) as 36.3 from the same paper. To complete the model we need three further standard deviations, (i) the residual standard deviation (taken as the larger of the two deviations computed from the Altman paper – 2.57) (ii) the intercept standard deviation (computed from Fig4 in Altman) as 11.31. For (iii) the time-by-treatment effect slope standard deviation, neither paper reports these values and so the main assumption for these power calculations are that this standard deviation will be at best equal to the residual standard deviation and at worst equal to the baseline mean standard deviation.

Study design: We assume that N-patients will be randomly assigned into two treatment groups (intervention/control), with N/2 receiving the anxiety intervention and N/2 receiving no such intervention. We further assume that the patients will have repeated equi-spaced visits=3 where the first visit is taken as baseline. We need to determine the N required for 80% power, if the true treatment effect is -4.65, as assumed above.

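### The primary outcome is tested for significance at every time point with no primary visit or decision rule, and the sample size names neither the visit nor the score scale

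*Protocol*

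**What the plan says.** Section 8.2.2, under the heading for the primary outcome, states: "Anxiety scores will be compared at each time point between the two groups for a statistically significant difference". It adds that the second and third time points use baseline-corrected scores, so the baseline comparison is on the raw score. Longitudinal modelling of all three time points appears only in the list of additional analyses.

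Table 1 in section 4.4 sets all three time points against the primary objective. Section 4.1 defines three measurements (baseline, first treatment, end of treatment) and says: "Scores at timepoints 1 & 2 will be corrected for baseline scoring for each participant". It ranks neither.

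Section 8.1 states: "The study is powered to detect a 10-point difference in patient-reported anxiety on the STAI". The calculation is for one test: "Based on an unpaired t-test with two groups of equal size". The assumptions it lists are power of 80%, alpha of 0.05 on two sides, SD 13 and a 10-point difference. The section concludes that "a total sample size of 54 (27 in each group) is required", raised to 60 for attrition. No visit is named, and the text does not say whether the 10 points and the SD of 13 refer to raw scores or to change from baseline.

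**The concern.** The sample size assumes one test at 5%. The analysis section prescribes a test at each visit, two of them after the intervention, and ranks none. Two things follow.

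- **Error rate.** Nothing stops a significant result at either post-baseline visit from being read as success, and that reading does not hold the false-positive rate at 5%.
- **No conclusion when visits disagree.** One consultation on the first treatment day could plausibly lower anxiety that day and not at the end of treatment, or the reverse. The protocol does not say what the trial would then conclude. In an unblinded 60-patient trial, a choice made after seeing the results could not be defended.

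The 80% power claim has the same gap: it attaches to no named comparison, and its value depends on the score scale that section 8.1 leaves open.

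**Working it through.** **Inputs**
- Two-sided alpha 0.05, 80% power, difference 10, SD 13, one unpaired t-test, 27 per group (section 8.1).
- Tests at each of three time points, the second and third baseline-corrected (section 8.2.2).
- Assumed, because the protocol does not give them: equal variance at each visit, a common within-patient correlation ρ between visits, and ρ from 0.3 to 0.7.

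**1. The plan's own figure**

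n per arm = 2 × (1.960 + 0.842)² × 13² / 10² = 2 × 7.849 × 1.69 = 26.5, so 27 per arm and 54 in total. Allowing for 10% attrition, 54 / 0.9 = 60. Both stated figures reproduce. Power from the exact t-test at 27 per arm is 79.2%. The arithmetic is sound for one test at 5%.

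**2. False-positive rate of the two post-baseline tests, if either counts as success**

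Independent tests: 1 − 0.95² = 9.75%.

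The two change scores share the same baseline, so they are not independent. With variance σ² at each visit and common correlation ρ:
- variance of each change score = 2σ²(1 − ρ)
- covariance of the two change scores = σ²(ρ − ρ − ρ + 1) = σ²(1 − ρ)
- correlation = σ²(1 − ρ) / [2σ²(1 − ρ)] = 0.5, whatever ρ is.

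The rate is then 1 − P(|Z₁| ≤ 1.96 and |Z₂| ≤ 1.96) for a bivariate normal pair:

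| Correlation between the two tests | Chance of at least one false positive |
|---|---|
| 0 | 9.75% |
| 0.5 (shared baseline, as derived) | 9.1% |
| 0.7 | 8.3% |
| 0.9 | 7.0% |

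**3. What the missing score scale does to the stated power**

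If 13 is the SD of a raw score, the SD of a change score is 13 × √[2(1 − ρ)]. The t-test power for 10 points at 27 per arm is then:

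| Assumed ρ | SD of change | Power |
|---|---|---|
| 0.3 | 15.4 | 65% |
| 0.5 | 13.0 | 79% |
| 0.7 | 10.1 | 95% |

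The stated power therefore carries over to a change score only if ρ is about 0.5.

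**4. The alternative of keeping both visits co-equal**

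With Bonferroni at 0.025 each: n per arm = 2 × (2.241 + 0.842)² × 1.69 = 32.1, so 33 per arm and 66 in total; 66 / 0.9 = 73.3, so 74 recruited. At the planned 27 per arm, t-test power for each visit would be 70%.

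**The case against.** **The statistical analysis plan may settle it.** Section 8.2 promises a detailed plan signed off before any analysis, and a testing order could be written there. Section 8.2.2 does not say that each comparison is an unadjusted 5% success criterion. This has some weight. But the protocol is not silent: it positively makes visit-by-visit significance tests the primary analysis, and it sizes the trial for one test.

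**Per-visit comparison is listed as exploratory.** Section 4.3.3 and Table 1 do list it so, and section 8.2.4 says exploratory outcomes are not tested for significance. That does not displace section 8.2.2, which places the per-visit tests under the primary outcome and the longitudinal analysis among the additional ones.

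**No success rule is stated.** This stands. The 9.1% assumes that either visit suffices. Requiring both would keep the error at or below 5%, with lower power. That neither rule is written is the defect itself.

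Four stronger readings are tempting but unsupported:
- A reader might count the baseline comparison as a third chance of success, which gives 1 − 0.95³ = 14.3% if the tests were independent. A baseline difference precedes the consultation and cannot support a claim of benefit, so this is not an efficacy error rate.
- A reader might see a substantive conflict in section 4.1, which corrects time points 1 and 2 where section 8.2.2 corrects the second and third. Correcting baseline for itself makes no sense, so this is most likely a numbering slip for the two post-baseline visits.
- A reader might take the appendix's slope difference ("if the true treatment effect is -4.65, as assumed above") as an effect per visit, combine it with the SD of 13, and call the trial underpowered at both visits. Section 8.1 presents the appendix as an independent method. Joining its slope to the SD in section 8.1 is a pairing that neither calculation uses.
- A reader might conclude that 54 is wrong. It reproduces.

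**Conclusion.** The point holds. The protocol prescribes two unranked post-baseline significance tests of the primary outcome, with no primary visit, decision rule or error control, against a sample size built for one.

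On the assumption that significance at either visit would count as success, the false-positive rate is about 9.1%, with a range of 7.0% to 9.75% as the correlation between the tests runs from 0.9 to 0. Apart from the error rate, discordant results would leave the trial without a conclusion.

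The 80% power belongs to no named comparison. If 13 is a raw-score SD and the analysis uses change scores, power for 10 points at 27 per arm runs from 65% to 95% for an assumed within-patient correlation of 0.3 to 0.7.

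The baseline significance test does not add to the efficacy error. It is simply uninformative, since under randomisation any baseline difference between arms is due to chance.

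**What to change.** - **Section 8.2.2:** name one post-baseline visit as the single primary comparison of baseline-adjusted STAI. The choice between first and last treatment is the sponsor's and should be made before any outcome data are seen. Test the other visit only if the primary one is significant (fixed sequence, each at two-sided 5%), or report it as secondary with a 95% CI.
- **Section 8.2.2, baseline:** replace the significance test with descriptive reporting, which section 8.2.1 already provides for the other baseline characteristics.
- **Section 4.1 and Table 1:** number the time points as in section 8.2.2 and mark which one is primary.
- **Section 8.1:** state that the 10-point/80% figure refers to the named visit. Say whether the SD of 13 is for raw or baseline-corrected scores and, if it is raw, which within-patient correlation is assumed.

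The cost is protocol wording, carried into the statistical analysis plan. The downside is that the other visit becomes conditional or secondary. With one named comparison, 54 (60 recruited) can stand, subject to the score-scale statement. Keeping both visits co-equal under Bonferroni would instead take about 66 patients, or 74 recruited.

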3.2. Design and bias considerations

The nature of the intervention makes it impossible to blind the patient or staff. However, data analysis will be undertaken on a pseudonymised basis. Participant selection bias will be present, with those patients wanting to know more self-selecting. It is not possible to account for this, however statistical analysis will be stratified by education and health literacy level (as well other sociodemographic data).

Figure 2: Study design flowchart

Illustrating flow of patients through the trial and the time points for data collection (3 time points numbered)

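### The sample size uses what appears to be a raw-score SD of 13, but the primary comparison uses undefined baseline-corrected scores; defining it as ANCOVA would remove the mismatch

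*Protocol*

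**What the plan says.** Section 8.1 gives the target, "The study is powered to detect a 10-point difference in patient-reported anxiety on the STAI", and the method: "Based on an unpaired t-test with two groups of equal size, assuming 80% power". The test is two-sided at 0.05 with SD 13, giving 54 patients (27 per arm), raised to 60 for 10% attrition. The SD was picked from a range of 10.2 to 15.6 in the US phase III trial of physicist consultations. Section 1 reports a criticism of that trial: it averaged anxiety at each time point and did not compare patients with their own baseline. That suggests 13 is a raw-score SD.

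The analysed quantity is described twice. Section 4.1 says follow-up scores will be "corrected for baseline scoring for each participant, and the average (mean) score across both trial arms compared". Section 8.2.2 says "The 2nd and 3rd timepoints will use baseline-corrected anxiety scores". Neither place says whether the correction is a subtraction or a regression adjustment.

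On covariates, section 6.3 says "Randomisation will be stratified by gender", but gender is not named in the primary comparison. Among the additional analyses, item b of section 8.2.2 says "Any baseline variables that appear, by chance, to differ between the groups will be added in as covariates". Section 3.2 says "statistical analysis will be stratified by education and health literacy level".

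**The concern.** A power statement holds only for the quantity and SD it was computed with. Correcting each patient's score and then comparing arm means describes a change score, whose SD depends on how strongly follow-up tracks baseline. That correlation is not given for the main calculation. If it is weak, the change score is noisier than the raw score, and 27 per arm no longer gives 80%.

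Analysis of covariance uses the same baseline measurement, removes the effect of chance baseline imbalance between small arms, and still compares patients with allowance for where they started. If the change score is what is meant, the plan gives up precision that is available from data it already collects.

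**Working it through.** **Inputs.** Difference 10, SD 13, two-sided 0.05, 27 per arm before attrition and 30 recruited (section 8.1). The baseline-to-follow-up correlation r is not stated there, so a range is shown. Assumption: the score SD is 13 at both visits.

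**The plan's own figure.** Normal approximation: n per arm = 2 × (1.960 + 0.842)² × 13² / 10² = 26.5, so 27 per arm and 54 in total; 54 / 0.9 = 60. The plan's arithmetic reproduces. Power at 27 per arm is 80.7% by this approximation and 79.2% by the exact noncentral t.

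**Change score.** Variance = 13² + 13² − 2r × 13², so SD = 13 × √(2(1 − r)). This equals 13 only at r = 0.5.

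**ANCOVA.** Residual SD = 13 × √(1 − r²). The change-score variance divided by the ANCOVA variance is 2(1 − r) / (1 − r²) = 2 / (1 + r).

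Power comes from the noncentral t with noncentrality 10 / (SD × √(2/n)). The degrees of freedom are 2n − 2 for the change score and two fewer for ANCOVA with baseline and gender. For example, at r = 0.3 the change-score noncentrality is 10 / (15.38 × 0.272) = 2.39, against 2.83 at SD 13.

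| r | Change SD | Change power, 27/arm | Change power, 30/arm | ANCOVA SD | ANCOVA power, 27/arm | Variance ratio |
|---|---|---|---|---|---|---|
| 0.3 | 15.38 | 65.0% | 69.7% | 12.40 | 82.8% | 1.54 |
| 0.4 | 14.24 | 71.6% | 76.3% | 11.91 | 85.6% | 1.43 |
| 0.5 | 13.00 | 79.2% | 83.4% | 11.26 | 89.3% | 1.33 |
| 0.6 | 11.63 | 87.3% | 90.6% | 10.40 | 93.4% | 1.25 |

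The change score reaches 80% at r = 0.51 with 27 per arm, and at r = 0.45 if all 30 per arm are evaluable (exact t). At r = 0.3 it would need 39 per arm; ANCOVA would need 26.

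Simulation with chance baseline imbalance (20,000 runs per value) agrees. At r = 0.3 ANCOVA has 82.1% and the change score 64.8%. At r = 0 ANCOVA has 78.8%, against 79.7% for the unadjusted comparison.

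**Appendix 1's inputs.** The appendix gives an intercept SD of 11.31, a residual SD of 2.57 and three slope SDs: 2.57, their mean 6.94, and 11.31. Assuming slopes independent of intercepts and visits at t = 0, 1, 2:

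- First treatment: r is 0.68 to 0.93, the change SD is 4.5, 7.8 or 11.9, and change-score power for 10 points at 27 per arm is at least 86%.
- Last treatment: r is 0.87, 0.61 or 0.43, the change SD is 6.3, 14.4 or 22.9, and power is essentially 100%, 71% or 35%.
- The slope of follow-up on baseline is 11.31² / (11.31² + 2.57²) = 127.9 / 134.5 = 0.95. In general the change-score variance exceeds the ANCOVA variance by (1 − slope)² times the baseline variance, here 0.05² × 134.5, or about 0.3. ANCOVA therefore gains almost nothing: the variance ratio is 1.00 to 1.02.

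**The case against.** The strongest reply is that no subtraction is stated. Section 8.2 defers detail to a statistical analysis plan that is not shown, and baseline-corrected could already mean ANCOVA. This stands as a limit on certainty. It does not clear the protocol, which fixes the analysed quantity in two places in words that lean towards a change score, and sizes the trial on something else.

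A second reply is that a randomised change-score comparison is unbiased and keeps its type I error, so the choice affects efficiency only. That is correct.

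Third, Appendix 1's inputs show no shortfall at first treatment, and at last treatment the shortfall comes from outcome spread that ANCOVA would not cure. This also stands. In the middle scenario r is 0.61 and power is still 71%, so the r = 0.5 threshold applies only when both visits have SD 13.

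The smaller points are limited too. Section 6.3 expects little variation of the outcome by gender, so adjusting for the stratum will change little. Item b concerns additional analyses, not the primary one. Education and health literacy do appear in section 4.3.2 and in item a of section 8.2.2, so section 3.2 is loosely worded and not an orphaned promise.

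**Conclusion.** The mismatch is real: the power statement and the described comparison do not refer to the same quantity, and the term linking them is undefined. With SD 13 at both visits and 27 evaluable per arm, change-score power runs from 65% to 87% as r goes from 0.3 to 0.6, against 83% to 93% for ANCOVA. For any r, ANCOVA is at least as precise apart from one or two degrees of freedom.

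A reader might infer that the trial is underpowered. The documents do not support that: r is not given, the 54 and 60 are correct for the test stated, and Appendix 1 points to high correlation at first treatment.

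A reader might also infer that ANCOVA guarantees 80%, or that 80% becomes a lower bound. Neither follows. At r = 0 exact power is 79.2%, and section 8.1 itself cites SDs up to 15.6. With a follow-up SD of 15.6 the residual SD falls to 13 only when r reaches √(1 − (13/15.6)²) = 0.55.

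**What to change.** - **Sections 4.1 and 8.2.2:** define the primary comparison as ANCOVA, or the equivalent mixed model, of post-baseline STAI on arm, baseline STAI and gender. Report the adjusted difference with its 95% confidence interval.
- **Section 8.1:** state that the power of about 80% is for an unadjusted score with SD 13. Add that ANCOVA is expected to match or exceed it (to within about 1 point when r is near 0) only if the follow-up SD is about 13. Do not call it a lower bound.
- **Section 8.2.2, item b (minor):** replace selection by observed imbalance with a prespecified covariate set for the sensitivity analysis, for example previous radiotherapy and number of fractions.
- **Section 3.2 (minor):** align the reference to stratified analysis with the subgroup and interaction analyses in sections 4.3.2 and 8.2.2 item a. It need not be deleted.

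The cost is wording in the protocol and the analysis plan. Section 6.2.2 already collects all the variables named, and no extra patients are needed. ANCOVA uses two more degrees of freedom than the t-test.
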